#### **10.5. Safety Analyses**

Safety will be evaluated for patients entered in the Phase I and Phase II portions of the study. The primary safety endpoint is tolerability of combination panobinostat and carfilzomib.

The analyses of safety will be based on the frequency of adverse events and their severity for patients in each cohort who received at least one dose of study treatment. Worst toxicity grades per patient will be tabulated for select adverse events and laboratory measurements by using NCI CTCAE criteria v4.0.

### **11. SAFETY REPORTING AND ANALYSES**

#### **11.1. Safety Analyses**

Safety assessments will consist of monitoring and recording protocol-defined adverse events (AEs) and serious adverse events (SAEs); measurement of protocol specified hematology, clinical chemistry, and urinalysis variables; measurement of protocol-specified vital signs; and other protocol-specified tests that are deemed critical to the safety evaluation of the trial drug.

#### **11.2. Adverse Events**

The PI is responsible for recognizing and reporting adverse events to the Sponsor. If not delegated it is the Sponsor's responsibility to report relevant SAEs to the applicable local, national, or international regulatory body.

##### **11.2.1. Definitions of Adverse Events**

An adverse event is the development of an undesirable medical condition, or the deterioration of a pre-existing medical condition following or during exposure to a medicinal product, whether or not considered causally related to the product.

An undesirable medical condition can be symptoms (e.g., nausea, chest pain), signs (e.g., tachycardia, enlarged liver), or the abnormal results of an investigation (e.g., laboratory findings).

### **11.2.2. Recording of Adverse Events**

All adverse events of any patient during the course of the trial will be reported in the case report form, and the investigator will give his or her opinion as to the relationship of the adverse event to trial drug treatment (i.e., whether the event is related or unrelated to trial drug administration). If the adverse event is serious, it should be reported immediately to the sponsor or designee. Other untoward events occurring in the framework of a clinical trial are also to be recorded as AEs (i.e., AEs that occur prior to assignment of trial treatment that are related to a protocol-mandated intervention, including invasive procedures such as biopsies, medication washout, or no treatment run-in).

All AEs regardless of seriousness or relationship to trial drug(s), spanning from the start of trial treatment, until 30 calendar days after discontinuation of protocol-specific treatment as defined by the protocol for that patient, are to be recorded on the corresponding case report form (CRF).

### **11.2.3. Abnormal Laboratory Values and Vital Signs**

The reporting of abnormalities of vital signs as adverse events should be avoided. Abnormalities of vital signs should not be reported unless any criterion for an SAE is fulfilled, the vital signs abnormalities cause the patient to discontinue trial treatment, or the investigator insists that the abnormality should be reported as an AE. Any grade 3 or 4 laboratory abnormalities or any clinically significant grade 1 or 2 hematology or biochemistry laboratory value(s) should be recorded as an AE. If an abnormal laboratory value or vital sign is associated with clinical signs and/or symptoms, the sign or symptom should be reported as an AE, and the associated laboratory value or vital sign should be considered additional information that must be collected on the relevant CRF.

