### 5.2.2. Definitions of Dose-Limiting Toxicity (DLT)

For the purpose of determining the MTD (see Section 5.2.3), DLT is defined as any of the following that are determined to be related to study treatment during **Cycle 1**:

- Grade 4 neutropenia (absolute neutrophil count [ANC] <500/ $\mu$ L) for >7 days.
- Febrile neutropenia (ANC <1000/ $\mu$ L with fever >101°F [38.5°C]).
- Grade 3 thrombocytopenia with  $\geq$  Grade 2 bleeding.
- Grade 4 thrombocytopenia (platelets <25,000/ $\mu$ L) > 7 days (patients may receive platelet support/transfusion).
- $\geq$  Grade 2 neuropathy with uncontrolled pain
- $\geq$  Grade 3 non-hematologic drug-related toxicity (excluding alopecia) despite optimal supportive care lasting >72 hours or requiring a dose reduction in the first cycle.
- Patients who are unable to receive 75% of the required doses of both agents secondary to toxicity.

Adverse events will be graded using the National Cancer Institute (NCI) Common Toxicity Terminology Criteria for Adverse Events v4.0 (CTCAE v4.0).

Dose modifications are not permitted during Cycle 1 in any cohort unless the subject experiences a DLT. Subjects in dose level -1 (see Table 2) who develop a DLT during Cycle 1 will be discontinued from the study. Subjects in dose level 1 or higher who experience a DLT during Cycle 1 will have treatment held. The DLT will be counted toward the assessment of the MTD for the given cohort; however, the subject may continue on therapy if the toxicity resolves and dose modifications can be implemented according to the dose modification guidelines in Section 6.0.

Patients who withdraw from the study before receiving 75% of their scheduled Cycle 1 doses due a non-drug related AE (i.e., tumor progression) will be considered inevaluable and will be replaced.

Patients without clinical evidence of progressive disease at the end of the first cycle of study therapy will continue treatment. Patients will be reevaluated for response after completing 2 cycles (8 weeks) of treatment. Patients with objective response or stable disease according the International Myeloma Working Group Uniform Response Criteria (see Appendix C) will continue treatment, with reevaluations until disease progression occurs, unacceptable toxicity develops, or the subject chooses to discontinue study treatment.

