**Table 8. Carfilzomib Dose Modifications for Non-Hematologic Toxicity**

Event	Action to be Taken
Allergic reaction/hypersensitivity Grade 2 – 3 Grade 4	Hold until ≤ Grade 1, reinstitute at full dose. Discontinue
Tumor lysis syndrome  (≥ 3 of following: ≥ 50% increase in creatinine, uric acid, or phosphate; ≥ 30% increase in potassium; ≥ 20% decrease in calcium; or ≥ 2-fold increase in LDH)	Hold carfilzomib until all abnormalities in serum chemistries have resolved. Reinstitute at full doses.
Infection Grade 3 or 4	Hold carfilzomib (no more than 3 weeks) until systemic treatment for infection complete. If no neutropenia, restart at full dose. If neutropenic, follow neutropenic instructions (Table 4).
Herpes zoster or simplex of any grade	Hold carfilzomib until lesions are dry. Reinstitute at full dose.
Neuropathy Grade 2 treatment emergent neuropathy with pain or Grade 3 neuropathy  Grade 4 neuropathy	Continue to dose. If neuropathy persists for more than two weeks hold carfilzomib until resolved to ≤ Grade 2 without pain. Then restart at 1 dose decrement  Discontinue carfilzomib
Renal Dysfunction  CrCl ≤ 30 mL/min	Hold until CrCl > 30 mL/minute; restart at 1 dose decrement
Congestive heart failure	Any subject with symptomatic congestive heart failure, whether or not drug related, must have the dose held until resolution or return to baseline, after which treatment may continue at a reduced dose, or the subject may be withdrawn from the study. If no resolution after 2 weeks, the subject will be withdrawn from the study.
Hypertension	All patients should be evaluated for hypertension and treated as needed. If hypertension cannot be controlled, reduce carfilzomib.

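### Section 11.2.3 requires no adverse-event entry for asymptomatic, non-serious hypertension, even at grade 3 or when carfilzomib is reduced, so the AE-based safety analysis may under-count it

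*Combined protocol and SAP*

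**What the plan says.** Section 11.2.3 sets the default for vital signs: "The reporting of abnormalities of vital signs as adverse events should be avoided". It then closes the list of exceptions. One is seriousness: "Abnormalities of vital signs should not be reported unless any criterion for an SAE is fulfilled". The other two are that the finding makes the patient stop study therapy, and that the investigator presses for an AE entry. If an abnormal reading comes with clinical signs or symptoms, the sign or symptom is the AE, and "the associated laboratory value or vital sign should be considered additional information that must be collected on the relevant CRF". Laboratory values get the opposite default in the same paragraph, repeated in Section 11.4.3: "Any grade 3 or 4 laboratory abnormalities or any clinically significant grade 1 or 2 hematology or biochemistry laboratory value(s) should be recorded as an" [adverse event].

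Table 8 (Section 6.3) has a row for hypertension. It calls for evaluation in all patients and treatment as needed, and adds: "If hypertension cannot be controlled, reduce carfilzomib". The amendment history shows that hypertensive events were added to this table in Amendment 5.

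Under Section 5.2.2, a treatment-related Cycle 1 event is a DLT if it is at least "Grade 3 non-hematologic drug-related toxicity (excluding alopecia) despite optimal supportive care lasting >72 hours or requiring a dose reduction in the first cycle". Hypertension is not excluded.

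Section 10.5 states: "The analyses of safety will be based on the frequency of adverse events and their severity". It adds worst-grade tabulations for selected AEs and laboratory measurements. Vital signs are not mentioned there.

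**The concern.** The protocol treats hypertension as important enough to change the carfilzomib dose, yet the AE rule tells sites by default to leave it out unless it is serious, ends treatment, or the investigator presses for it. A dose reduction is none of these. A reduction after Cycle 1 could therefore appear in the dosing record with no graded, causality-assessed event to explain it.

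Safety is a secondary objective (Section 2.2), and tolerability of the combination is the primary safety endpoint (Section 10.5). Both are read from AE counts. A recording rule that discourages one class of event pushes its reported frequency down. The same applies to other abnormalities found only as vital-sign readings, such as a slow pulse or low blood pressure without symptoms. Levels 5 and 6 use carfilzomib at 56 mg/m² (Table 3), the highest dose in the protocol, so a complete blood-pressure record matters when those levels are described.

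**Working it through.** No arithmetic applies: the plan gives no figure on this point and no hypertension rate. The check is to follow each kind of hypertension event through the text.

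**Inputs.** The vital-sign rule, its exceptions and the laboratory rule (Section 11.2.3); the AE definition (11.2.1) and recording rule (11.2.2); the hypertension row of Table 8; the DLT definition (5.2.2) and DLT assessment (Section 5); the planned safety analysis (10.5); the visit schedule (7.3.1 and 7.3.5).

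**Outcome by case under Section 11.2.3.**

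| Hypertension event | AE entry required? |
|---|---|
| Meets an SAE criterion | Yes |
| Causes discontinuation of trial treatment | Yes |
| Accompanied by clinical signs or symptoms | The sign or symptom is the AE; the reading goes on the CRF as additional information |
| Asymptomatic, non-serious, grade 3, treated but with no discontinuation | No, unless the investigator insists |
| Asymptomatic, non-serious, leading only to a carfilzomib hold or reduction | No, unless the investigator insists |
| Asymptomatic, non-serious, meeting the DLT definition | Counted as a DLT under 5.2.2; AE entry not required by 11.2.3 unless the patient discontinues or the investigator insists |

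The last three rows are the gap.

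**Comparison with the other recording rules.** Section 11.2.1 includes signs among adverse events and gives tachycardia, a vital-sign finding, as an example. Section 11.2.2 requires all AEs on the CRF whatever their seriousness or relationship to drug. Section 11.2.3 removes most vital-sign findings from that requirement. A grade 3 potassium value must be an AE; a grade 3 blood pressure need not be.

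**Is there another route into the safety tables?** Laboratory values have one, because Section 10.5 tabulates their worst grades directly. Vital signs do not. Blood pressure is measured at each Cycle 1 treatment visit (7.3.1) and on Days 1, 8 and 15 of later cycles (7.3.5), and Section 11.1 lists vital signs among the safety assessments, but no analysis of the readings is planned. A stored reading carries neither a CTCAE grade nor the investigator's opinion on causality.

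**Does the DLT count depend on Section 11.2.3?** No. Section 5 has patients assessed for DLT at each Cycle 1 visit before treatment. Section 5.2.2 counts the DLT toward the MTD without reference to the AE reporting rule. It also bars Cycle 1 dose modification unless a DLT has occurred, so a Cycle 1 reduction made per protocol already has a declared DLT behind it.

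**The case against.** The best defence is that Section 11.2.3 limits the listing of abnormal readings and does not reach hypertension as a condition. Table 8 names hypertension as an event to be evaluated and treated. Section 11.2.1 defines an AE as an undesirable medical condition. Section 11.4.1 prefers a recognised diagnosis to its component signs, and Section 11.4.6 calls for an entry when a pre-existing condition worsens. An investigator who starts treatment or reduces carfilzomib may well record hypertension on those grounds, and may in any case insist under Section 11.2.3. The SAE definition in Section 11.3.1 also takes in important medical events that may need intervention. Laboratory and vital-sign findings may legitimately be handled differently.

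These points narrow the gap but do not close it. No sentence says that hypertension handled under Table 8 falls outside the vital-sign rule, and a site reading that rule literally would leave it out. Two sites could record the same event differently, each with support in the text.

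The defence does rule out two stronger inferences. A reader might conclude that such hypertension never reaches the safety data. The documents do not support that: symptoms are reported, readings and concomitant medications are collected, and the investigator has discretion. A reader might also conclude that a DLT could be missed and an escalation decision changed. Sections 5 and 5.2.2 assess and count DLTs independently of Section 11.2.3, so that does not follow.

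**Conclusion.** The point holds in a limited form. Section 11.2.3 does not require an AE entry for asymptomatic, non-serious hypertension that is grade 3, needs treatment, or leads to a carfilzomib hold or reduction. Entry rests on the investigator's discretion, and Section 10.5 has no vital-sign analysis to make up the difference. Hypertension may therefore be under-counted in the AE tables. For DLTs, what may be missing is the supporting AE record, not the count.

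The direction of the bias is clear, but its size is not. A number of lost events would need an assumed hypertension rate and an assumed share that is non-serious, asymptomatic, not leading to discontinuation and not reported by choice; the documents supply none of these. The conclusion assumes only that some sites follow Section 11.2.3 as written. It should be corrected because the sections conflict and the remedy is cheap.

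**What to change.** Rewrite the vital-sign part of Section 11.2.3 so that it agrees with Sections 11.2.1, 11.2.2 and 5.2.2 and with Table 8. Require that a vital-sign abnormality be recorded and graded as an AE if any of these applies:

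- it is CTCAE grade 3 or higher;
- it is clinically significant;
- it leads to treatment, a dose hold or a dose reduction;
- it meets the DLT definition.

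Keep the existing triggers for SAE criteria and discontinuation. State expressly that hypertension handled under Table 8 is always recorded, and put the same instruction in the CRF completion guidance. No dose-modification or DLT rule needs to change.

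The cost is one protocol paragraph and a guidance note. The downside is a few more AE entries and a slightly higher reported AE rate.

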### **11.2.4. Handling of Adverse Events**

All adverse events resulting in discontinuation from the trial should be followed until resolution or stabilization. Patients must be followed for AEs for 30 calendar days after discontinuation of protocol-specific treatment (e.g., chemotherapy, radiation, oral medications, targeted therapy, and surgery). All new AEs occurring during this period must be reported and followed until resolution unless, in the opinion of the investigator, these values are not likely to improve because of the underlying disease. In this case, the investigators must record his or her reasoning for this decision in the patient's medical record and as a comment on the CRF. After 30 days, only AEs, SAEs, or deaths assessed by the investigator as treatment related are to be reported.

## **11.3. Serious Adverse Events**

### **11.3.1. Definitions of Serious Adverse Events**

The definitions of serious adverse events (SAEs) are given below. The principal investigator is responsible for ensuring that all staff involved in the trial are familiar with the content of this section.

An SAE or reaction is defined as any untoward medical occurrence that: results in death, is immediately life-threatening, requires at least a 24-hour in-patient hospitalization or prolongation of existing hospitalization, results in persistent or significant disability/incapacity, or is a congenital anomaly/birth defect.

The definition of SAE also includes any important medical event. Medical and scientific judgment should be exercised in deciding whether expedited reporting is appropriate in other situations, such as important medical events that may not be immediately life-threatening or result in death or hospitalization, but may jeopardize the patient or may require intervention to prevent one of the other outcomes listed in the previous definition. These should also usually be considered serious. Examples of such events are intensive treatment in an emergency room or at home for allergic bronchospasm; blood dyscrasias or convulsions that do not result in hospitalization; or development of drug dependency or drug abuse. Death due to disease progression will be recorded on the CRF and as an SAE up to 30 days post the last dose of trial drug.

Treatment within or admission to the following facilities is not considered to meet the criteria of “in-patient hospitalization” (although if any other SAE criteria are met, the event must still be treated as an SAE and immediately reported):

- Emergency Department or Emergency Room
- Outpatient or same-day surgery units
- Observation or short-stay unit
- Rehabilitation facility
- Hospice or skilled nursing facility
- Nursing homes, Custodial care or Respite care facility

Hospitalization during the trial for a pre-planned surgical or medical procedure (one which was planned prior to entry in the trial), does not require reporting as a serious adverse event to the Sponsor.

### **11.3.2. Serious Adverse Event Reporting by Investigators**

It is important to distinguish between “serious” and “severe” adverse events, as the terms are not synonymous. Severity is a measure of intensity; however, an AE of severe intensity need not necessarily be considered serious. For example, nausea which persists for several hours may be considered severe nausea, but may not be considered an SAE. On the other hand, a stroke which results in only a limited degree of disability may be considered only a mild stroke, but would be considered an SAE.

Severity and seriousness should be independently assessed when recording AEs and SAEs on the CRF.

Adverse events classified by the treating investigator as **serious** require expeditious handling and reporting to the sponsor in order to comply with regulatory requirements. Serious adverse events may occur at any time from the start of trial treatment through the 30-day follow-up period after the last trial treatment. The sponsor must be notified of all SAEs, regardless of causality, within one business day of the first knowledge of the event by the treating physician or research personnel.

To report a SAE, the appropriate CRF pages should be completed with the necessary information. The CRF pages required for SAE reporting include:

- Adverse Event and Safety Complementary pages
- Trial drug dosing
- Concomitant Medications
- Demographics
- Medical History

All SAEs and medically confirmed deaths (regardless of causality assessment) occurring on trial treatment or within 30 days of last trial treatment must be reported to the sponsor as SAEs within the CRF and followed until resolution (with autopsy report if applicable).

Deaths occurring 30 days after last trial treatment that are deemed 'possibly' or 'probably' related to trial drug must be reported as SAEs within the CRF (with an autopsy report if available).

Deaths occurring 30 after last trial treatment and not attributed to trial treatment (e.g., disease progression) need not be reported as SAEs, but simply captured on the appropriate CRF.

The investigator must review and sign off on the SAE data within the CRF. The SAE will be reported to the sponsor or designee as outlined in the Safety Monitoring Plan.

Follow-up information for SAEs and information on non-serious AEs that become serious should also be reported to the sponsor or designee as soon as it is available; these reports should be submitted using the CRF. The detailed SAE reporting process will be provided to the sites in the Safety Monitoring Plan.

Investigators must report SAEs and follow-up information to their responsible Institutional Review Board (IRBs)/Ethics Committee according to the policies of the responsible IRB/IEC.

Contact details for SCRI Innovations Sponsor Safety department are as follows:

[contact]

[contact]

### **11.3.3. Novartis Instructions for Rapid Notification of Serious Adverse Events**

The Sponsor has the obligation to report all SAEs to Novartis Pharmaceuticals Clinical Safety and Epidemiology Department (CS&E), and to report SAEs to the FDA and IRB as applicable. All events reported to the FDA are to be filed utilizing Form FDA 3500A (MedWatch Form), or other approved form.

All events must be reported by fax to Novartis Pharmaceuticals CS&E Department within 24 hours of learning of its occurrence. This includes serious, related, unlabeled (unexpected) adverse experiences. All deaths during treatment or within 30 days following completion of active protocol therapy must be reported within 1 business day of learning of its occurrence. Reports should be faxed to:

**Novartis Pharmaceuticals  
Clinical Safety and Epidemiology Dept.**

[contact]

Any SAE occurring until 4 weeks after the patient has stopped study participation must be reported. This includes the period in which the study protocol interferes with the standard medical treatment given to a patient (e.g., treatment withdrawal during washout period, change in treatment to a fixed dose of concomitant medication).

Serious adverse events occurring more than 4 weeks after study discontinuation need only be reported if a relationship to the Novartis study drug (or therapy) is suspected.

### **11.3.4. Safety Reporting for Studies Done Under an IND**

All written IND Safety Reports submitted to the FDA by the Sponsor must also be faxed to:

Novartis Pharmaceuticals  
Clinical Safety and Epidemiology Dept.  
[contact]

---

Onyx Drug Safety and Pharmacovigilance  
**Onyx [contact]

### **11.3.5. Onyx Instructions for Reporting Serious Adverse Events**

All relevant SAEs will be reported to the competent authority, other applicable regulatory authorities, and participating investigators, in accordance with ICH guidelines, FDA regulations, and/or local regulatory requirements by the Sponsor.

All SAEs will be submitted to Onyx within 24 hours of learning of the events.

